STUDY PROTOCOL INCLUDING STATISTICAL ANALYSIS PLAN

OFFICIAL TITLE: Guanfacine Clinical Trial for Smoking Cessation

BRIEF TITLE: Guanfacine Clinical Trial for Smoking Cessation ([name], PI)

CLINICALTRIALS.GOV ID: NCT02051309

PROTOCOL DATE: October 7, 2021

Identifying effective medications for the treatment of tobacco dependence remains a high priority as the vast majority of smokers fail to maintain long-term abstinence even with FDA approved pharmacotherapies. One promising, yet relatively unexplored avenue for medication development for smoking cessation are medications which target stress-reactivity. Several lines of evidence suggest that stress is a primary mediator of smoking maintenance and relapse. Preclinical research demonstrates that noradrenergic pathways are involved in stress-induced reinstatement to nicotine, as well as nicotine-related reinforcement and withdrawal, and that their manipulation may be of potential therapeutic benefit for smoking cessation.

Guanfacine is an alpha2a adrenergic receptor agonist known to attenuate stress-induced reinstatement to alcohol and other drugs of abuse in preclinical studies. Guanfacine rescues the prefrontal cortex from detrimental effects of stress and improves working memory, attention, and behavioral control. In a study evaluating 3mg/day guanfacine for smoking cessation, we demonstrated that guanfacine was well tolerated, attenuated the effects of stress on smoking, reduced smoking-related reinforcement, improved cognition, and significantly reduced smoking during a brief treatment phase.

STUDY OBJECTIVE

To conduct a Phase II clinical trial evaluating the efficacy of guanfacine for smoking cessation. Using a double-blind, placebo-controlled, parallel group design, we randomized adult daily smokers to guanfacine (6mg/day ER, or placebo) combined with brief behavioral support for an 8-week treatment period.

STUDY DESIGN AND METHODS

This Phase II, clinical trial is a double-blind, placebo-controlled, parallel group study. Adult daily smokers motivated to quit smoking were be randomized to guanfacine (6mg day ER) or placebo Sex will be a stratification variable (50% female). Following eligibility screening and randomization, participants were titrated to steady state medication levels over a 3-week period. Participants completed an 8-week treatment period combining medication with brief behavioral support and were followed 6 months post-treatment to assess the durability of medication effects. The primary outcome measure was rates of prolonged smoking abstinence at the end of the 8-week treatment phase.

ELIGIBILTY

Minimum Age: 18 Years

Maximum Age: 65 Years

Sex: All

Gender Based:

Accepts Healthy Volunteers: Yes

Criteria:

Inclusion Criteria:

Age 18-65

Able to read, write and comprehend English

Smoker

Able to take oral medications and willing to adhere to a medication regimen

Provide evidence of a stable living residence in the last 2 months, have reasonable transportation to the study site, and have no plans to move within the next 3 months or unresolved legal problems

Exclusion Criteria:

Any significant current medical conditions that would contraindicate smoking

Current Diagnostic and Statistical Manual of Mental Disorders (DSM-IV) abuse or dependence of other substances, other than nicotine dependence or alcohol abuse

Positive test results at intake appointment on urine drug screen for illicit drugs

Past 30 days use of any psychoactive drugs including anxiolytics and antidepressants

Women who are pregnant or nursing

Suicidal, homicidal or evidence of current mental illness such as schizophrenia, bipolar disorder or major depression, or anxiety disorders

Meeting DSM-IV criteria for current attention deficit hyperactivity disorder (ADHD)

Individuals who are currently taking medications known to be effective for smoking cessation or are regular users of other tobacco products in the past 30 days

Only one member per household can participate in the study

Specific exclusions for administration of guanfacine not already specified include:

EKG evidence at baseline screening for any clinically significant conduction abnormalities or arrhythmias

Known intolerance for guanfacine or any alpha blocker

History of fainting, syncopal attacks

Heart failure or myocardial infarction

Impaired liver (as indicated by aspartate aminotransferase (AST), alanine aminotransferase (ALT) >3x normal)

Renal function (as indicated by estimated creatinine clearance <60cc/min)

Treatment with any antihypertensive drug or any alpha-adrenergic blocker

Use of any central nervous system depressant (e.g., phenothiazines, barbiturates, benzodiazepines)

Use of strong cytochrome P450 3A4 (CYP3A4) inhibitors (e.g., ketoconazole) or inducers (e.g., rifampin), or consumption of grapefruit juice

Subjects may not have donated blood in the past 8 weeks or have been involved in other investigational studies that involve substantial blood draws or medications unknown to us

STATISTICIAL CONSIDERATIONS

PRIMARY HYPOTHESIS: Guanfacine vs placebo will increase rates of prolonged abstinence during weeks 3 to 8 of the 8-week treatment period. Logistic regression was used to evaluate medication effects on the abstinence outcome.

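### Does the primary abstinence window need a stated day 1, set against titration and a quit date?

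*Combined protocol and SAP*

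**What the plan says.** The outcome is described in two places. Study Design and Methods states: "The primary outcome measure was rates of prolonged smoking abstinence at the end of the 8-week treatment phase". The primary hypothesis under Statistical Considerations supplies the span: "Guanfacine vs placebo will increase rates of prolonged abstinence during weeks 3 to 8 of the 8-week treatment period". The analysis follows directly: "Logistic regression was used to evaluate medication effects on the abstinence outcome".

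The schedule is in Study Design and Methods, in two consecutive sentences. The first reads: "Following eligibility screening and randomization, participants were titrated to steady state medication levels over a 3-week period". The next begins: "Participants completed an 8-week treatment period combining medication with brief behavioral support and were followed 6 months post-treatment". The Study Objective is shorter. It has participants randomized to drug or placebo "combined with brief behavioral support for an 8-week treatment period" and does not mention titration.

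The only reference to quitting as an intention is the description of the population: "Adult daily smokers motivated to quit smoking". No quit day is given, and the event that opens week 1 is not named.

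**The concern.** A prolonged-abstinence endpoint is defined by its window, and a window needs an origin. Here the design section gives only the closing time, the opening week appears in another section, and week 1 is not tied to randomization, first dose, the end of titration or a quit day. If titration took up the first three of the eight weeks, a window opening in week 3 would open while participants were still being titrated. The trial would then be judging abstinence partly before the intended drug level was reached. Someone replicating or pooling the result could also place the window, and the end of treatment, three weeks away from where they really were. Since this is the only primary outcome stated, that is worth checking.

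**Working it through.** The plan gives no sample size, event rate, power or significance level, so it has no figure to reproduce. The check is a day count and a comparison of the texts.

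**Inputs from the document:** titration 3 weeks; treatment period 8 weeks; window weeks 3 to 8.

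**Assumptions, not in the document:** titration starts on day 1 and lasts the full 21 days; if it lies inside the treatment period, it fills weeks 1 to 3; there is no gap between titration and week 1 if titration comes first.

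**Lengths**
- Titration: 3 × 7 = 21 days.
- Treatment period: 8 × 7 = 56 days.
- Window from the start of week 3: days 15 to 56 of the period, 56 − 14 = 42 days.
- Window from the end of week 3: days 22 to 56, 56 − 21 = 35 days.

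**Placement, counted from the start of titration**

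| Titration | Window opens | Window days | Days in titration (days 1–21) |
|---|---|---|---|
| Before the 8 weeks | Start of week 3 | 36–77 | 0 of 42 |
| Before the 8 weeks | End of week 3 | 43–77 | 0 of 35 |
| Within the 8 weeks | Start of week 3 | 15–56 | 7 of 42 (17%) |
| Within the 8 weeks | End of week 3 | 22–56 | 0 of 35 |

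Overlap with titration therefore ranges from 0 to 7 days, and only one of the four combinations gives any. With the window opening at the start of week 3, the two placements share days 36 to 56, which is 21 of 42 days (50%). The end of treatment moves from day 77 to day 56, or 21 days.

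**Which placement the text supports.** The design paragraph lists events in the order they happen: screening and randomization, titration, the treatment period, follow-up. Titration has its own sentence and its own duration, ahead of the eight weeks. The rival reading rests on the Study Objective, a one-sentence summary that leaves titration out and does not place it inside the eight weeks.

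**Whether the two outcome statements conflict.** They do not. Abstinence sustained over weeks 3 to 8 is known at the end of week 8, which is when the design section says the outcome is taken.

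**Whether a quit day is needed.** It affects interpretation, not classification. With the window opening on day 15, a quit day on day 1, 8 or 15 implies 15 − 1 = 14, 15 − 8 = 7 or 15 − 15 = 0 days of grace. The window is the same in each case, because it is defined in treatment weeks.

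**Follow-up.** It is counted from the end of treatment, which is the right origin for durability. The interval is the same under either placement; only its distance from randomization moves.

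**The case for a change.** The best case for a change is that no sentence excludes the rival reading. The design paragraph has no linking word such as then or afterwards. The Study Objective can be read as eight weeks from randomization, and describing the treatment period as medication plus support does not rule out titration weeks. Even with titration first, a reader cannot tell whether the two weeks left out are a grace period after a quit day. The sponsor knows the answer, and one sentence would give it.

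All of that is right as a description of what is missing. What does not follow is a consequence. The objection does not show that any participant would be classified wrongly or that the arms would be treated differently. Titration is described for participants generally in a double-blind trial, so whichever calendar was used should apply to both arms alike. The document is dated October 2021 and is written mostly in the past tense, so an added sentence would record a schedule already run. The low cost of that sentence is a reason it could do no harm, not evidence that the plan goes wrong without it.

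**Conclusion.** The omission is real and minor, and the plan can stand. On the reading that the design paragraph supports, the window opens after titration, none of its days fall within it, and the endpoint is sound. The 17% overlap arises only if titration fills weeks 1 to 3 of the treatment period and the window opens on the first day of week 3; the plan states neither. The effect of either placement on abstinence rates or power cannot be derived from the document.

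This conclusion rests on two assumptions: that the design paragraph is in time order, and that the analysts counted weeks on the visit calendar the trial actually used. Both are ordinary, and nothing in the text contradicts them.

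### Does a 3-month no-move criterion undermine a trial whose participants are followed for about 37 weeks?

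*Combined protocol and SAP*

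**What the plan says.** One inclusion criterion deals with residence and access together. Its opening part reads "Provide evidence of a stable living residence in the last 2 months, have reasonable transportation to the study site", and it ends by requiring that participants "have no plans to move within the next 3 months or unresolved legal problems". The word next places the start of the 3 months at the eligibility assessment. The document states no purpose for the criterion.

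Study Design and Methods sets out the course of participation. After screening and randomization, "participants were titrated to steady state medication levels over a 3-week period". Then: "Participants completed an 8-week treatment period combining medication with brief behavioral support". Afterwards they "were followed 6 months post-treatment to assess the durability of medication effects".

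On the endpoint, the same section says: "The primary outcome measure was rates of prolonged smoking abstinence at the end of the 8-week treatment phase". The primary hypothesis under Statistical Considerations narrows this: "Guanfacine vs placebo will increase rates of prolonged abstinence during weeks 3 to 8 of the 8-week treatment period". The only analysis named is a logistic regression of the abstinence outcome. No hypothesis or analysis is given for the 6-month follow-up, and neither a sample size nor an expected attrition rate is stated.

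**The concern.** Set side by side, the two durations do not match. A criterion about moving house, in the same sentence as stable residence and transport to the site, reads like a safeguard for retention, yet it ends long before participation does. Someone who says at screening that they will move in month 4 is eligible as written.

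The 6-month follow-up is the trial's only stated evidence on durability, and the introduction motivates the work by the failure of most smokers to stay abstinent in the long term. If planned movers dropped out of that follow-up, there would be a cost either way. Counting them as smoking would lower both abstinence rates and shrink the difference. Leaving them out would reduce the sample and make it more selected.

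**Working it through.** **Inputs.** From the Inclusion Criteria: a 3-month no-move horizon. From Study Design and Methods: 3 weeks of titration, 8 weeks of treatment, 6 months of follow-up, and a primary outcome at the end of treatment. One month is 365.25 / 12 / 7 = 4.348 weeks, so 3 months is 13.0 weeks and 6 months is 26.1 weeks. The plan states no total duration, so there is no figure of its own to reproduce.

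**Step 1: calendar.** Titration most naturally comes before the 8 weeks, but both readings were tried.

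| | Titration before the 8 weeks | Titration within the 8 weeks |
|---|---|---|
| End of treatment and primary outcome | 3 + 8 = week 11 | week 8 |
| Total participation | 11 + 26.1 = 37.1 weeks | 8 + 26.1 = 34.1 weeks |
| Horizon left after treatment ends | 13.0 - 11 = 2.0 weeks | 13.0 - 8 = 5.0 weeks |
| Follow-up beyond the horizon | 37.1 - 13.0 = 24.0 of 26.1 weeks (92%) | 34.1 - 13.0 = 21.0 of 26.1 weeks (81%) |

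Weeks are counted from randomization and rounded after calculation. Screening time, whose length is not stated, comes off the 2.0 or 5.0 weeks. On either reading the horizon spans titration, treatment and the weeks 3 to 8 abstinence window, with a small allowance for screening, and leaves most of the follow-up uncovered.

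**Step 2: does moving mean loss?** This step is needed before the mismatch can do harm, and the document does not supply it. It says that participants were followed, without saying whether contacts were in person, by telephone or by mail. It has no rule that ends participation on a move, and a move may be local.

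**Step 3: size if every mover were lost.** All inputs here are assumptions: 100 per arm, 6-month abstinence of 10% versus 20%, two-sided 5% test, a share m of each arm moving, and every mover counted as smoking. Both rates are then multiplied by (1 - m). With d the difference, p the mean of the two rates p1 and p2, and n = 100, power is Φ{[d - 1.96·√(2p(1-p)/n)] / √([p1(1-p1) + p2(1-p2)]/n)}.

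| m | Rates | Difference | Power | Odds ratio |
|---|---|---|---|---|
| 0 | 10.0% vs 20.0% | 10.0 points | 51% | 2.25 |
| 5% | 9.5% vs 19.0% | 9.5 points | 48% | 2.23 |
| 15% | 8.5% vs 17.0% | 8.5 points | 44% | 2.20 |

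For m = 15%, the odds ratio is (0.17/0.83) / (0.085/0.915) = 2.20. The risk ratio stays at 2.0 throughout. Power falls by 2 to 7 points. With unpooled variance in the test it runs from 52% to 49% and 44%, which gives the same fall.

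**Step 4: could the arms differ?** Allocation is randomized and double-blind, and a plan already held at screening precedes allocation. Nothing in the document suggests that planned moves would be unequal between arms.

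**The case for a change.** The best case for the concern is that the mismatch is real on either reading of the timetable, that the criterion visibly serves access to the site, and that no other stated safeguard covers the later months. Loss that is balanced between arms still costs precision, and under a missing-equals-smoking rule it pulls the difference toward zero. A longer horizon, or agreement to remote follow-up, would be cheap to write.

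The calendar part of this stands. The rest does not make it an error:

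- A horizon matched to the treatment phase and the primary outcome is coherent, and no other statement in the document contradicts it.
- The fall of 2 to 7 points is an upper figure for the assumed range of movers. It needs every mover to be lost and every mover to have held a plan they would disclose at screening. An eligibility rule about plans cannot touch unplanned moves.
- Stretching the horizon to 9 months would exclude people with ordinary moving plans. That gives up recruitment and generalisability for a gain on durability that cannot be quantified from the document.
- Waiving the 3-month rule for anyone who accepts remote follow-up would admit people who move during treatment. It would still place no condition on someone who moves in month 4.
- The document describes randomization, follow-up and analysis largely in the past tense, so an eligibility change could hardly alter who was enrolled.

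**Conclusion.** The concern does not hold as an error in the plan. The no-move horizon of about 13 weeks covers titration, treatment and the primary outcome (week 11 from randomization at the latest), provided screening takes no more than about 2 weeks. It does not cover 81-92% of the 6-month follow-up, but nothing in the document says that a participant who moves is lost. Even if all movers were lost, the assumed figures give a fall in power of 2 to 7 points on an outcome for which no test is specified, with no sign of bias between arms. How long the horizon should be is a matter of design preference.

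A narrower point survives: the document does not describe how follow-up contacts were made or how missing follow-up outcomes were counted. That is missing detail, and changing the 3 months would not supply it.

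### Do the one-word smoking criterion and the exclusion of conditions that contraindicate smoking put the wrong people in the trial?

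*Combined protocol and SAP*

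**What the plan says.** The objective reports that "we randomized adult daily smokers to guanfacine" or placebo. The Study Design and Methods section adds motivation: "Adult daily smokers motivated to quit smoking were be randomized to guanfacine" or placebo.

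The eligibility section follows directly. Its five inclusion items cover age, English, smoking, medication and residence. The smoking item is the single word Smoker. The nearest thing to motivation is "Able to take oral medications and willing to adhere to a medication regimen", which is about taking the tablets and not about quitting.

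The first exclusion is "Any significant current medical conditions that would contraindicate smoking". A later one, whose window is counted in days, removes "Individuals who are currently taking medications known to be effective for smoking cessation or are regular users of other tobacco products in the past 30". Drug-related medical exclusions have their own heading, "Specific exclusions for administration of guanfacine not already specified include".

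The aim is cessation: "To conduct a Phase II clinical trial evaluating the efficacy of guanfacine for smoking cessation". The endpoint is abstinence: "The primary outcome measure was rates of prolonged smoking abstinence at the end of the 8-week treatment phase".

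**The concern.** There are two separate worries.

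**The inclusion item.** Screening staff apply the list, not the design paragraph. Taken alone, the list would pass someone who smokes occasionally, or who does not want to quit. If such people abstain, or fail to, regardless of treatment, they dilute the drug effect. They also make the placebo abstinence rate hard to interpret, and a reader could not reconstruct who was eligible.

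**The exclusion.** A rule built on whether smoking is medically acceptable suits a study that asks people to smoke. This trial asks them to stop. Read literally, the rule removes people with a strong medical reason to quit, and the document gives no reason for it. Safety exclusions specific to guanfacine are listed elsewhere, so the item does not seem needed for that purpose. The price would be a narrower population to which the result applies.

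**Working it through.** **Step 1: compare the criteria with the stated population.** The list has 5 inclusion and 19 exclusion items (9 general, 10 under the guanfacine heading), 24 in all.

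| Element of the stated population | Where stated | Criteria that implement it |
|---|---|---|
| Adult | Objective; design | 1 (age 18-65) |
| Smoker | Objective; design | 1 (one word) |
| Daily | Objective; design | 0 of 24 |
| Motivated to quit | Design | 0 of 24 |

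The list therefore leaves out two elements that the text supplies. No criterion says the opposite, for example by admitting non-daily smokers.

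**Step 2: does the exclusion conflict with anything?** Only 1 of the 19 exclusions turns on a contraindication to smoking, and no other passage contradicts it. The design has a 3-week titration and a placebo arm, and the primary hypothesis counts abstinence over weeks 3 to 8. Some participants may therefore go on smoking for weeks, and some throughout. Leaving out people for whom that is medically unacceptable is a plausible reason. This is inference, because the document states none.

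**Step 3: could dilution be large?** There is no figure in the plan to reproduce: it gives no sample size, power, expected rates or non-daily share. Every input below is an assumption: 100 per arm; daily smokers abstaining at 15% on placebo and 30% on drug; non-daily smokers abstaining at 40% on placebo; non-daily share *f* of 0 to 0.3; two-sided 5% test of two proportions with pooled variance under the null.

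Arm rate = (1 − *f*) × daily rate + *f* × non-daily rate.

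Power = Φ[(d − 1.96 × s0)/s1], where d = p1 − p0, p̄ = (p0 + p1)/2, s0² = 2p̄(1 − p̄)/n and s1² = [p0(1 − p0) + p1(1 − p1)]/n.

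- *Scenario A:* no drug effect in non-daily smokers (40% in both arms).
- *Scenario B:* the same odds ratio in both groups. OR = (0.30/0.70)/(0.15/0.85) = 2.43. The non-daily odds on drug are 2.43 × 0.40/0.60 = 1.62, a rate of 61.8%.

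| *f* | Placebo | A: drug | A: difference (points) | A: power | B: drug | B: difference (points) | B: power |
|---|---|---|---|---|---|---|---|
| 0 | 15.0% | 30.0% | 15.0 | 72% | 30.0% | 15.0 | 72% |
| 0.1 | 17.5% | 31.0% | 13.5 | 61% | 33.2% | 15.7 | 73% |
| 0.2 | 20.0% | 32.0% | 12.0 | 49% | 36.4% | 16.4 | 73% |
| 0.3 | 22.5% | 33.0% | 10.5 | 38% | 39.5% | 17.0 | 74% |

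The sample size matters too. Under A, moving *f* from 0 to 0.3 takes power from 50% to 25% at 60 per arm, from 88% to 53% at 150, and from 95% to 65% at 200.

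The sign of the effect on power thus rests on one unsupported choice, whether the drug works in non-daily smokers. The rest depends on an invented sample size, invented rates and an invented non-daily share. Unmotivated smokers cannot be sized at all.

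**Step 4: validity.** The design places eligibility screening before randomization. A loose or narrow criterion applies to both arms alike, so it affects whom the result describes and perhaps precision. It does not bias the treatment comparison.

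**The case for a change.** The best case for acting is that the eligibility list is the only operative statement of who may enter, and nothing marks a redaction there. A design sentence is no substitute for a screening rule. The primary analysis is a logistic regression with no stated adjustment for baseline smoking or motivation, so a mixed population would go straight into the endpoint. The repair would cost two lines of text.

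Some of this stands. The list is incomplete, and a reader cannot tell from it what smoking frequency or motivation was required. It is also fair to say that the reason for the exclusion is missing.

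The inference of harm does not stand. The document is written largely in the past tense and reports that daily smokers were randomized. Nothing in it shows that a non-daily or unmotivated smoker entered. If enrolment is over, new criteria would change nobody's eligibility, and what is left is a matter of description. For the exclusion, a rule about conditions that contraindicate participation would be vaguer than the present one and close to circular. Saying that the present rule removes smokers with smoking-related disease also overstates an item limited to significant current conditions.

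**Conclusion.** No change to the plan follows. The inclusion item is a gap that the same document fills: the objective and design text name the population, and anyone running or reading the trial would take the one-word criterion in that sense. The exclusion is a fair trade-off between who is studied and who might be put at risk while still smoking. It narrows generalisability by an amount the documents do not allow anyone to compute, and it leaves the randomized comparison intact.

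No effect on power is established. The fall from 72% to 38% needs 100 per arm, the assumed rates, a 30% non-daily share and a drug that does nothing in those smokers. With an equal odds ratio instead, power is 74%.

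This conclusion assumes that the people enrolled match the design description, as the document says. Evidence that non-daily or unmotivated smokers were enrolled would be worth reporting alongside the results. Beyond that, stating the smoking and motivation criteria applied, and the reason for the exclusion, is a matter of clarity only.

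### Do the exclusions for alpha-blocker intolerance and for conditions that contraindicate smoking conflict with the trial's drug and purpose?

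*Combined protocol and SAP*

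**What the plan says.** The introduction gives the drug's class: "Guanfacine is an alpha2a adrenergic receptor agonist". The Study Objective section gives the purpose: "To conduct a Phase II clinical trial evaluating the efficacy of guanfacine for smoking cessation". Study Design and Methods describes the population as "Adult daily smokers motivated to quit smoking".

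The Eligibility section has two layers of exclusions. The general list opens with "Any significant current medical conditions that would contraindicate smoking". A second list follows under the lead-in "Specific exclusions for administration of guanfacine not already specified include". That list contains "Known intolerance for guanfacine or any alpha blocker", together with EKG abnormalities, fainting or syncope, heart failure or infarction, liver and renal limits, central nervous system depressants and CYP3A4 interactions. Among these it also has "Treatment with any antihypertensive drug or any alpha-adrenergic blocker". No reason is given for either of the two criteria in question.

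**The concern.** There are two separate worries.

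- **Intolerance criterion.** A blocker and an agonist act in opposite directions. If the criterion was meant to catch people who tolerate guanfacine's class badly, it names the wrong class. A person with known intolerance to another alpha2 agonist could then be randomised and titrated. That would be a safety matter, and it could cause early drop-out in the active arm only.
- **Smoking criterion.** A cessation trial that turns away people for whom smoking is medically inadvisable seems to exclude smokers with the strongest reason to quit. The test is also smoking, not the study drug or participation in the trial. The result might then not apply to an important group.

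**Working it through.** No arithmetic applies. Neither criterion enters a sample size, a rate or a test, and the documents give no count of people excluded under either. The check is to set the passages side by side.

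**Intolerance criterion**

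1. The introduction says what guanfacine is. The criterion says who may not be enrolled. These are different statements, and they conflict only if an exclusion must share the drug's class. Nothing in the documents says so.
2. The criterion has two limbs. The first covers guanfacine itself, so known intolerance to the study drug is excluded. The second adds a further group and takes nothing away from the first.
3. Alpha-adrenergic blockers appear twice in the guanfacine-specific list: once for past intolerance and once, more fully named and beside antihypertensives, for current treatment. A second, fuller mention is more easily read as a deliberate choice of class than as a typing error. The list also contains syncope and cardiac exclusions, so a precaution about blood pressure is a possible motive. Both readings are inferences, because the plan states no motive.
4. The gap that remains is a person who is intolerant of a different alpha2 agonist, has no known intolerance to guanfacine, and is not caught by any other exclusion. For this gap to do harm, three things must hold: such people enrol in relevant numbers, their intolerance carries over to guanfacine, and they then suffer harm or leave treatment. The documents support none of the three.

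**Smoking criterion**

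1. The wording is limited to conditions that are both significant and current. It does not remove every smoker with a smoking-related illness.
2. Participants enter as daily smokers. Study Design and Methods describes a 3-week titration, and the primary hypothesis under Statistical Considerations counts abstinence in weeks 3 to 8 of the 8-week treatment period. Smoking while on study is therefore foreseeable, at least early on, and a safety reason for the criterion is possible, though unstated.
3. Narrowing entry in this way restricts the population. It does not contradict the aim of testing efficacy in the smokers who are enrolled.

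**Effect on the comparison**

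Study Design and Methods places eligibility screening ahead of titration and treatment, and both criteria concern facts known at screening. They apply before anyone is allocated, so they cannot differ by arm. The randomised contrast between guanfacine and placebo among those enrolled is unaffected, as are the abstinence endpoint and the logistic regression.

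**The case for a change.** The strongest reply is that the mismatches are real and unexplained. Excluding current treatment with an alpha blocker does not cover past intolerance in someone now untreated, and the syncope and EKG criteria catch only some forms of intolerance. The introduction reports tolerability at 3 mg/day, whereas this trial uses 6 mg/day ER, so the screen for intolerance is not trivial. As for smoking, the drug's own risks have a separate list, and no smoking session run by the study is described. The earlier study did measure stress effects on smoking and smoking-related reinforcement, so the line may have been carried over from work of that kind. The criterion also names no conditions, so a reader cannot tell who was turned away.

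Part of this stands. The wording of the smoking criterion is odd for a cessation trial, neither criterion has a stated reason, and a person intolerant of another alpha2 agonist is not excluded by name. The carry-over from earlier work is conjecture. The higher dose makes tolerability matter more, but it does not show that intolerance to a related drug predicts trouble with guanfacine. How drop-out in the active arm would be handled is a question about the analysis, and rewording this criterion would not answer it.

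**Conclusion.** The concern does not hold. The intolerance criterion contradicts no other part of the document, and the harm attributed to it depends on class carry-over and drop-out for which the documents offer no support. The smoking criterion limits generalisability at most. Whether to widen it is an eligibility preference that trades breadth against safety, and which class or condition either criterion ought to name is a clinical matter that the documents cannot settle.

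The size cannot be computed. Neither criterion biases the treatment comparison, and the number of people excluded is unknown. This conclusion assumes that both criteria were applied at screening, before allocation, as Study Design and Methods indicates. It does not depend on the inferred motives being right. The document describes randomisation, treatment and analysis largely in the past tense, so new wording could not change who was enrolled. A stated reason for each criterion would help a reader judge to whom the result applies, but its absence is missing detail and not a flaw in the plan.
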